10. STATISTICAL ANALYSIS PLAN

Statistical analysis will be performed by tenured [name] in Biostatistics. [name] is involved in all statistical aspects of our lab including power calculations, secure data storage, data synthesis/ interpretation and guidance regarding analytical/quantitative techniques. In addition, we encourage all junior members of our laboratory to gain proficiency in analytical methods such that investigators emerge from the laboratory with both biological as well as statistical skills. [name] is eager to help mentor our junior members to ensure that these goals are achieved. [name] has developed an interest in sleep science through our interactions and is a strong member of our team. In all cases we are adequately powered to assess the impact of sex as a biological variable which will be an important exploratory goal of our study, given known sex differences in sleep disorders, Alzheimer's, and tau. Moreover, we are careful to control for various covariates including age, gender, BMI and ApoE status (which is part of the PHS score). We recognize that ApoE status may be a risk factor for OSA as well as AD and may have complex interactions with OSA effects on memory, making careful analyses of interactions important.

Aim 1: Although all major pathophysiological traits will be assessed, our primary outcome is to compare the loop gain of older OSA patients (age 65-85 years) with the loop gain of carefully matched individuals without

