OSA. We will assess our predictors of oxygen responsiveness to extend our recent publications⁵⁰. We have powered this analysis using our preliminary data based on a mean loop gain difference of 2.1 with standard deviation 0.4 using an unpaired t test with $\alpha=0.05$ and $\text{power}>0.8$. We will also analyze age as a continuous variable within the 20 year range. Our sample size will be adequate to adjust for any covariates (if matching is inadequate or other relevant covariates are imbalanced) and will provide participants for the other aims in which oxygen responsive OSA patients are required. We will also model the various pathophysiological traits (as previously described²⁶⁰) to determine how loop gain, upper airway gain, arousal threshold, and pharyngeal anatomy interact¹³⁵. This aim will provide a rich data set for further analyses/signal processing^{250,251,262,263} and characterizing thoroughly participants in the subsequent aims. For **Aim 2**, we will quantify the apnea hypopnea index (using criteria independent of desaturation) on 2 l/min supplemental O₂ vs sham (room air) in patients with varying underlying endotypes. We have powered this analysis based on our preliminary data using a $\text{power}>0.8$ and $\alpha=0.05$ with a change in AHI of 20/h (a clinically important difference) with standard deviation 5/h. We will also assess changes in neurocognitive function (Aim 2, VPA primary neurocognitive outcome).

The interpretation should be straightforward. If we confirm a major subset of OSA patients who are oxygen responsive, we will extend our recent findings that we can identify these patients based on underlying pathophysiology. If oxygen therapy lowers both loop gain and AHI then this finding would support our assertion that loop gain is causally important in a subset of OSA patients and that oxygen is a viable therapeutic approach.

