[name], PhD, who is an expert neuropsychologist. We anticipate that we will see smaller hippocampal volume in OSA vs. controls although this finding will depend to some extent on the magnitude of the memory impairment in Aim 2. Our use of amyloid and tau quantification will be of major interest given the novelty in OSA. We expect the extent of tau within the region of interest to be higher in participants with OSA. We will also explore how tau relates to improvement of learning with OSA therapy. We are also optimistic that beta-amyloid neuritic plaque density may be a robust outcome metric for future longitudinal studies. We can clearly determine how various neurocognitive abnormalities correspond with MR and PET findings^{184,316,317}.

Aim 4: [name] our Co-I Tenured [name] will oversee these analyses for our pilot clinical trial although the PI and the Co-Is (including [name] for AD) have considerable clinical trial experience as well. We will compare the results of the word pairs test with 3 months of O2 vs. PAP therapy (n=60 total completing). We will use an intention to treat analysis such that all randomized patients will be included and any dropouts will be analyzed using last observation carry forward. We powered this analysis based on our preliminary data with a treatment related difference of 6.9% (a clinically relevant difference) and sd=2.2% assuming alpha=.05 and power>0.8. Although we will compare O2 to PAP, we will also assess within-subject changes with treatment. For treatment, we will perform an efficacy analysis since we anticipate that despite our best efforts adherence will be imperfect. We will analyze other neurocognitive variables as well in an exploratory manner, but are not powered for multiple comparisons. We will also compare preferences with therapy via structured exit interviews to understand how best to optimize a large multicenter comparative effectiveness trial if our results are indeed compelling^{318,319}. We will adjust for covariates (eg. age, BMI, sex, PHS score) if imbalanced after randomization.

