11. HUMAN SUBJECTS

We will enroll 260 participants for the protocol.

Aim 1— Overnight Visit #1

We anticipate that 130 subjects will complete Overnight visit #1.

Aim 2 — Overnight Visit #2 and #3

Of the 130 subjects that complete Aim 1, 65 subjects who have been identified to have obstructive sleep apnea will complete Overnight visit #2-#3.

Aim 3 — Imaging Visit #1

Of the 20 subjects that complete Aim 1 and Aim 2, the same participants will be invited to complete Imaging

Visit #1. We will attempt to enroll all 20 subjects. Additionally, 20 subjects without OSA, who completed overnight visit 1, will be invited to complete the imaging visit. In total, we will recruit 40 subjects for this aim.

Aim 4 — 3 month Trial of Supplemental O2 or PAP therapy

Of the 130 subjects that completed Aim 1, 60 obstructive sleep apnea oxygen sensitive subjects will be invited to complete a 3-month trial of supplemental oxygen or PAP therapy. Subjects that complete the trial will return for Morning Visit 1.

[figure not shown]

Figure 3. Schematic of study visits and participants to be enrolled per aim.

Inclusion:

1. Age 65-85 years
2. Gender: Men or Women
3. MOCA > 26
4. Independently living and able to drive
5. OSA (AHI \geq 5/h) or no OSA
6. Subjects must consent to waiving their right to obtain their PHS score (since the score is not yet actionable and could lead to social stress and ethical dilemmas)

Exclusion:

1. Currently smoking
2. History of COPD or asthma
3. Heart Failure Class III or IV, unstable cardiovascular disease, or uncontrolled hypertension
4. Neuromuscular Disease
5. Drowsy Driving (ESS > 18/24)
6. Inability to complete study procedures, such as questionnaire that are only available/validated in English
7. Lack of decisional capacity to provide informed consent
8. Participants in whom magnetic resonance imaging Magnetic Resonance Imaging [MRI] is contraindicated including, but not limited to, those with a pacemaker, presence of metallic fragments

near the eyes or spinal cord, or cochlear implant

9. Presence of a brain tumor or lobar stroke
10. Current drug or alcohol abuse/dependence
11. Prisoners

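### Aim 4 lets imbalance seen after randomisation decide covariate adjustment, contradicts the plan's own general statement, and omits the baseline word-pairs score

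*Combined protocol and SAP*

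**What the plan says.** All of the following is in section 10, Statistical Analysis Plan.

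- **Aim 4:** "We will adjust for covariates (eg. age, BMI, sex, PHS score) if imbalanced after randomization". No threshold for imbalance and no regression model is named. Within-subject change is mentioned as an additional assessment, but no baseline word-pairs score appears among the covariates.
- **Opening paragraph, covering all aims:** "we are careful to control for various covariates including age, gender, BMI and ApoE status (which is part of the PHS score". This carries no condition. It also lists ApoE, where Aim 4 lists the PHS score.
- **Aim 1:** loop gain in older OSA patients is compared "with the loop gain of carefully matched individuals without" OSA. The power statement is "based on a mean loop gain difference of 2.1 with standard deviation 0.4 using an unpaired t test". Adjustment is mentioned as something the sample size permits: "Our sample size will be adequate to adjust for any covariates (if matching is inadequate or other relevant covariates are imbalanced". Neither the matching variables nor the type of matching (individual pairs or frequency) is stated.

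**The concern.** In a randomised comparison any baseline imbalance is due to chance, so its presence is a poor reason to adjust. The sound reason is that a covariate predicts the outcome. A rule triggered by imbalance chooses the model after the arms have been seen. Without a criterion and with an open list, it does not fix which model that is. The general statement at the head of the section points the other way, so an analyst can cite the plan for either an adjusted or an unadjusted estimate.

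The omitted covariate is the natural one: the same participant's word-pairs performance before treatment. The plan describes Aim 4 as a pilot that will inform later studies, so the precision and reproducibility of the estimate matter whatever the p-value.

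Aim 1 raises a smaller version of the same issue. Controls are matched, but the matching variables enter the analysis only if the matching is judged to have failed.

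**Working it through.** **1. The plan's own power figure.** Aim 4 inputs are a difference of 6.9%, SD 2.2%, alpha 0.05 and 60 completers. I assume a two-sided test and 30 per arm, since neither is stated.

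- Standardised effect: 6.9 / 2.2 = 3.14 SD.
- 80% power needs 2 per arm (normal approximation) or 3 per arm (exact t, power 81.5%).
- At 30 per arm power is about 1.00. The claim of power above 0.8 is therefore true, although these inputs do not generate 60; that is a separate matter.
- The effect with 80% unadjusted power at 30 per arm is 0.736 SD, or 0.736 × 2.2% = 1.6%.

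**2. What a baseline score could add.** If the untreated score correlates rho with the outcome, ANCOVA multiplies the variance of the treatment difference by 1 − rho². Estimating p covariates costs an expected factor of (N − 3)/(N − p − 3). The documents give no rho, so the values below are assumed, and covariates beyond the baseline score are taken to add nothing.

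At N = 60 the cost is 57/54 = 1.056 for p = 3 (baseline, age, sex) and 57/52 = 1.096 for p = 5 (baseline, age, sex, BMI, PHS). Effective N is 60 / [(1 − rho²) × cost].

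| rho | 1 − rho² | Effective N, no cost | p = 3 | p = 5 |
|---|---|---|---|---|
| 0.3 | 0.91 | 66 | 62 | 60 |
| 0.5 | 0.75 | 80 | 76 | 73 |
| 0.7 | 0.51 | 118 | 111 | 107 |

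Break-even for p = 3 is rho = √(1 − 54/57) = 0.23.

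**3. A smaller trial.** Section 7 estimates that about 30% of elderly OSA patients respond to oxygen. Applied to the 65 OSA participants in section 11, that is 0.30 × 65 = 19.5, or roughly 10 per arm. Section 11 itself plans for 60. At N = 20 the net variance factors at rho 0.3, 0.5 and 0.7 are:

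- p = 3 (cost 17/14 = 1.214): 1.11, 0.91, 0.62.
- p = 5 (cost 17/12 = 1.417): 1.29, 1.06, 0.72.

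A long covariate list can therefore lose precision, which argues for a short one.

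**4. Conditional against fixed adjustment.** Simulation used 30 per arm, 8,000 runs per cell and four covariates jointly correlated rho with the outcome. Imbalance was declared at p<0.05 or p<0.20, and the true effect was 0.736 SD or zero.

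| rho | Power, always adjust | Power, adjust if imbalanced |
|---|---|---|
| 0.3 | about 81% | 79–80% |
| 0.5 | about 87% | 80–81% |
| 0.7 | about 97% | 81–85% |

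With no true effect, the mechanical imbalance rule gave type I error of 2.7–5.0%, so no inflation. Freely reporting the smaller of the adjusted and unadjusted p-values gave 6.7–9.0%.

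**5. Which score can serve as baseline.** Section 9 schedules word pairs in the evening and morning around Overnight 1, which is untreated, and around Overnights 2 and 3, one of which is on room air. The start-of-treatment morning test follows a night on the assigned device, so it is already post-treatment. A home sleep test may replace Overnight 1 (sections 9 and 21). Word pairs are listed only under overnight and treatment visits, so those participants may lack an Overnight 1 score.

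**6. Aim 1.** 2.1 / 0.4 = 5.25 SD. With 65 OSA participants out of "We anticipate that 130 subjects will complete Overnight visit #1", and 65 controls assumed, power is about 1.00.

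**The case against.** The strongest reply is that the consequences are limited, and much of it stands.

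- A reader might infer that the whole plan adjusts only when imbalance appears. The opening paragraph of section 10 says otherwise. The defect is an unreconciled inconsistency, not a uniformly conditional plan.
- A reader might infer that matched Aim 1 groups will be analysed by an unpaired t test with inflated standard errors. The documents do not say so: that test is named only in the power sentence, and Aim 1 also provides for adjustment, age as a continuous variable and modelling of the traits. Pair precision is lost only under individual matching, which is never stated, so no standard-error figure can be given.
- A reader might infer that the aims are underpowered or the type I error inflated. On the stated inputs power is near 1.00, and a mechanical imbalance rule did not inflate error.
- No document gives a baseline–outcome correlation. If the endpoint is overnight change in recall, rho may be low; section 7 attributes up to 80% of the variance in consolidation to sleep quality. Below about 0.23, with three covariates at N = 60, adjustment costs a little precision.

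What this does not answer is that Aim 4 names no criterion and no model, so the reported estimate remains the analyst's choice. Nor does near-certain power settle the matter: section 10 itself allows that a null result could reflect inadequate power.

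**Conclusion.** The point holds for Aim 4. Adjustment depends on imbalance observed after randomisation, with an open list, no criterion and no baseline word-pairs score, and this conflicts with the unconditional statement at the head of section 10. Different estimates can be reported under the same plan, and most of the precision available from a prognostic baseline is forgone.

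The size is conditional on assumed correlations. With baseline, age and sex at N = 60, the gain is worth about 2, 16 or 51 extra patients at rho 0.3, 0.5 or 0.7 (62, 76 and 111 against 60). The possible downside is a small loss if rho is low, or a larger one if recruitment falls well short. Neither aim drops below its stated power on its own inputs. The change is worth making because it is cheap and fixes the primary estimate in advance. Aim 1 is a secondary point, with no magnitude claimed.

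**What to change.** **Aim 4.** Delete the imbalance condition and reconcile the paragraph with the opening of section 10, including whether ApoE or PHS is meant where genetic risk is used. State the primary analysis as an ANCOVA of the 12-week word-pairs outcome on arm, always adjusting for:

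- one defined untreated word-pairs score, measured in the same way as the outcome: Overnight 1, or the Aim 2 room-air night when a home test replaced Overnight 1, but not the start-of-treatment morning score;
- a short fixed set such as age and sex.

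Add a rule for a missing baseline score. Other covariate sets can be labelled as sensitivity analyses.

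**Aim 1.** State the matching variables and whether matching is individual or by frequency. Analyse loop gain by regression on OSA status that always includes the matching variables, or by a paired analysis if matching is individual, in place of the condition "if matching is inadequate or other relevant covariates are imbalanced".

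**Cost.** A few sentences in the SAP and no new visits. Each added covariate costs about 2% of precision at N = 60. Some participants may lack an Overnight 1 score, which is why the fallback and the missing-baseline rule are needed.

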11. HUMAN SUBJECTS

We will enroll 260 participants for the protocol.

Aim 1— Overnight Visit #1

We anticipate that 130 subjects will complete Overnight visit #1.

Aim 2 — Overnight Visit #2 and #3

Of the 130 subjects that complete Aim 1, 65 subjects who have been identified to have obstructive sleep apnea will complete Overnight visit #2-#3.

Aim 3 — Imaging Visit #1

Of the 20 subjects that complete Aim 1 and Aim 2, the same participants will be invited to complete Imaging

Visit #1. We will attempt to enroll all 20 subjects. Additionally, 20 subjects without OSA, who completed overnight visit 1, will be invited to complete the imaging visit. In total, we will recruit 40 subjects for this aim.

Aim 4 — 3 month Trial of Supplemental O2 or PAP therapy

Of the 130 subjects that completed Aim 1, 60 obstructive sleep apnea oxygen sensitive subjects will be invited to complete a 3-month trial of supplemental oxygen or PAP therapy. Subjects that complete the trial will return for Morning Visit 1.

[figure not shown]

Figure 3. Schematic of study visits and participants to be enrolled per aim.

Inclusion:

1. Age 65-85 years
2. Gender: Men or Women
3. MOCA > 26
4. Independently living and able to drive
5. OSA (AHI \geq 5/h) or no OSA
6. Subjects must consent to waiving their right to obtain their PHS score (since the score is not yet actionable and could lead to social stress and ethical dilemmas)

Exclusion:

1. Currently smoking
2. History of COPD or asthma
3. Heart Failure Class III or IV, unstable cardiovascular disease, or uncontrolled hypertension
4. Neuromuscular Disease
5. Drowsy Driving (ESS > 18/24)
6. Inability to complete study procedures, such as questionnaire that are only available/validated in English
7. Lack of decisional capacity to provide informed consent
8. Participants in whom magnetic resonance imaging Magnetic Resonance Imaging [MRI] is contraindicated including, but not limited to, those with a pacemaker, presence of metallic fragments

near the eyes or spinal cord, or cochlear implant

9. Presence of a brain tumor or lobar stroke
10. Current drug or alcohol abuse/dependence
11. Prisoners

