6. SPECIFIC AIMS

Aim 1: We will assess the endotypes (mechanisms) underlying OSA in elderly individuals known to be high risk for AD (vs. non-OSA matched controls) using novel recently validated simplified techniques which do not require burdensome complex overnight experiments to assess endotypes (primary outcome loop gain). We will further assess the predicted response to O2 therapy in terms of respiratory outcomes among elderly OSA patients with varying levels of loop gain and pharyngeal collapsibility.

Hypothesis 1: A substantial proportion of high AD risk patients with OSA should be O2 responsive as predicted using pathophysiological assessments.

Aim 2: We will perform an overnight mechanistic study of oxygen therapy vs. room air in high AD risk patients with OSA (recruited from Aim 1 and others if necessary). Given the frequent intolerance of PAP in elderly patients, we anticipate that oxygen therapy may be a viable therapeutic approach in this fragile population. We will focus on respiratory outcomes (primary outcome: apnea hypopnea index) but also assess sleep dependent memory consolidation on word pairs task given the major impact in the elderly.

Hypothesis 2: O₂, compared to room air, will improve OSA and neurocognitive outcomes in select elderly OSA patients at risk of AD.

Aim 3: Preclinical AD with OSA and non-OSA controls, from Aim 1 will have structural and molecular brain imaging focusing on hippocampal atrophy as a predictor of memory consolidation. We will also assess amyloid and tau in the medial temporal region as function of OSA severity and as a predictor of neurocognitive function. This aim will lay the groundwork for designing a robust clinical trial using neuroimaging outcomes.

Hypothesis 3: Impairment in memory consolidation is a function of hippocampal size in OSA patients at risk of AD.

Aim 4: We will perform a pilot randomized trial of oxygen vs. PAP therapy in OSA patients with preclinical AD.

Hypothesis 4: In preclinical AD with OSA, oxygen will be a viable therapeutic strategy to improve memory.

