7. BACKGROUND AND SIGNIFICANCE

Several lines of evidence suggest a potential causal link between sleep disruption and Alzheimer's disease (AD). First, a large prospective observational study showed an increased incidence of AD among patients with untreated obstructive sleep apnea (OSA). Second, a prominent paper in Science recently showed accumulation of tau with sleep disturbance in mice as well as humans. The authors further observed increased tau pathology spreading with chronic sleep disturbance. Third, common genetic links have been observed between OSA and AD e.g. ApoE related. Fourth, we and others have observed substantial memory impairment with sleep fragmentation which is amenable to OSA therapy. Of note, the recent identification of markers of those at risk for AD including the polygenic hazard score (PHS) have made early interventional studies (or prevention) more feasible i.e. to bend the curve of AD progression by delaying or reducing cognitive decline, rather than trying to prevent fully established disease. Advances in human brain imaging also allow assessment of tau and amyloid which are thought to be pathogenic in AD, and can now be identified prior to symptomatic onset, i.e., in the preclinical phase. Thus, the investigation of sleep disorders as a therapeutic target to change AD trajectory and to improve well-being in those afflicted is clearly required.

Importance of OSA: OSA is an increasingly common condition with well established neurocognitive and cardiometabolic sequelae. Major risk factors for OSA such as aging and obesity are also on the rise contributing to the high prevalence of OSA. While debate continues regarding the impact of OSA, definitive data have now established major sequelae of OSA independent of known confounders. Regarding neurocognitive outcomes, we and others have shown that OSA leads to impaired memory consolidation, particularly that which occurs overnight with sleep (i.e., sleep dependent memory consolidation). Studies have suggested a link of OSA to AD although definitive data are still lacking.

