9. RESEARCH DESIGN AND METHODS

After written informed consent has been obtained, the following procedures will be undertaken:

Daytime Visit 1

Participants will be asked to complete the following:

1. *Polygenic hazard score (PHS)*—a genetic assessment that predicts the age onset of Alzheimer’s Disease through a saliva sample. The saliva sample kit will be provided to a Clinical Laboratory Improvement Amendments (CLIA) certified lab to obtain the PHS. The PHS is derived from an analysis of a 31 single-nucleotide polymorphism panel (including ApoE). After samples are processed by the lab, they will not be retained. Samples will not be shared with other researchers or institutions, other than the lab, which is processing and destroying the sample after results have been obtained.
2. *Montreal Cognitive Assessment (MoCA)*—a screening tool for mild cognitive impairment and early stages of Alzheimer’s.
3. *Anthropomorphic assessment:* A basic exam, including height, weight, blood pressure, and oxygen saturation will be obtained (from clinical chart, if available).

4. *Questionnaires:* Standard sleep questionnaires will be completed Epworth Sleepiness Scale (ESS), Pittsburgh Sleepiness Questionnaire Inventory (PSQI), Insomnia Sleepiness Index (ISI), and Morningness-Eveningness questionnaire (MEQ). In addition, participants will complete the Geriatric Depression Scale (GDS) to identify depression. If action needs to be taken in response to suicidality, a plan of action will be described in Item 15.
- 5.

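### The aims concern high-AD-risk and preclinical-AD patients, but no rule defines or selects either group, so the results cannot speak to preclinical AD

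*Combined protocol and SAP*

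**What the plan says.** Section 6 (Specific Aims) names the populations. Aim 1 studies "elderly individuals known to be high risk for AD". Aim 2 compares "oxygen therapy vs. room air in high AD risk patients with OSA". Aim 3 applies the preclinical AD label to the people it images. For Aim 4 the text reads: "We will perform a pilot randomized trial of oxygen vs. PAP therapy in OSA patients with preclinical AD". Hypothesis 4 repeats the preclinical AD label.

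Section 7 (Background) presents PHS as a marker of AD risk. It says of brain amyloid and tau that they "can now be identified prior to symptomatic onset, i.e., in the preclinical phase".

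Section 11 (Human Subjects) lists six inclusion criteria: age 65-85, either sex, MoCA above 26, living independently and able to drive, OSA or no OSA, and "Subjects must consent to waiving their right to obtain their PHS score". None of the 11 exclusions concerns AD risk. Section 9 obtains PHS at Daytime Visit 1: "The saliva sample kit will be provided to a Clinical Laboratory Improvement Amendments (CLIA) certified lab to obtain the PHS". No threshold or decision follows from the result.

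**The concern.** Each aim carries a label that goes beyond age and OSA status, and Section 7 names the tools that would establish it. If those tools never decide who enters, the label describes an intention and not the people studied. Followed exactly, the plan would answer Hypotheses 3 and 4 in people whose AD risk was not a condition of entry. Their results would still be reported under a preclinical AD heading and carried into the imaging study and the multicentre trial that Section 10 says this work should inform.

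**Working it through.** No sample size, power or alpha stated in the plan belongs to this point, so the main check is textual. I looked at every place where a selection on AD risk could sit.

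1. **Eligibility (Section 11).** The one criterion naming PHS withholds the score from the participant. It sets no value or percentile. The only cognitive criterion, MoCA above 26, selects people who screen as unimpaired.
2. **PHS collection (Section 9, Daytime Visit 1).** The sample is taken after consent, and nobody is kept or dropped on the result.
3. **Recruitment (Section 12).** The chart search filters on OSA status and age. The advertisements ask for ages 65-85. The Brain Health Center is one source among several, with no risk criterion attached.
4. **Aim 4 entry (Section 9, 3-month trial).** AHI above 15/h and expected benefit from nocturnal oxygen; no AD-risk condition.
5. **PET (Sections 9 and 11).** Imaging comes after Overnight 1, so it is an outcome and not a screen. Section 11 plans 20 people with OSA and 20 without. Even if all 20 scanned OSA patients entered Aim 4, 60 - 20 = 40 of its 60 participants (67%) would have no scan. Section 9 also assigns the single tracer, MK-6240, to amyloid in one sentence and to tau in the next, so amyloid status is not clearly obtained even in the 40.
6. **Statistical plan (Section 10).** ApoE, as part of PHS, is a covariate, with a general statement that its interactions with OSA deserve careful analysis. In Aim 4, PHS is adjusted for only if it turns out imbalanced.
7. **One pool, two labels.** Section 11 draws Aim 4 from the same 130 who complete Aim 1. The pool is called high risk in Aims 1-2 and preclinical in Aims 3-4, with no step between that would turn one into the other.

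I then asked whether a size could be put on any dilution of effect. Assumptions: two-sided alpha 0.05, equal allocation, and an effect present only in a fraction f of one group. The documents give no f. Power is approximately Φ(fδ / (σ√(2/n)) - 1.96).

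- *Aim 3 amyloid* (δ = 0.2, σ = 0.18, n = 20 per group): σ√(2/n) = 0.0569. At f = 1, 0.2/0.0569 = 3.51 and power is 94% (93% by noncentral t), which agrees with the plan's claim of more than 80%. At f = 0.8 it is 80%; at f = 0.3 it is 18%.
- *Aim 4 word pairs* (δ = 6.9, σ = 2.2, n = 30 per arm): σ√(2/n) = 0.568. At f = 0.3, 2.07/0.568 = 3.64 and power is 95%. If the standard deviation also rises because responders and non-responders are mixed, σ = √(2.2² + 0.3 × 0.7 × 6.9²/2) = 3.14 and power is 71% (noncentral t).

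The answer runs from negligible to serious depending on an f that the documents do not supply. No figure for dilution can be defended from them.

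**The case against.** Five arguments count on the other side.

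- **Age and OSA may themselves be the risk.** Section 7 cites a higher incidence of AD in untreated OSA, and Section 7 also describes the people who might benefit as older, at risk and without major impairment. This gives Aims 1-2 a possible reading of high risk, though an unstated one. It does not rescue preclinical AD in Aims 3-4, which Section 7 ties to imaging.
- **The interpretation text is modest.** For Aims 1, 2 and 4, Section 10 speaks of subsets of OSA patients or selected patients, and Aim 4 is called a pilot. That stands, but Hypothesis 4 still states its claim for preclinical AD.
- **AD-risk interactions are already intended.** Section 10 does say this for ApoE. The intention is general and names no term, outcome or estimate.
- **Enrolling 260 for 130 completers might hide a PHS screen.** No text says so, and MoCA failure, withdrawal or the home sleep test option would explain the gap equally well.
- **Figures 2 and 3 and a few pages were not readable in the copy used here.** A selection step shown only there cannot be excluded. The numbered eligibility list is complete and has none.

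A reader might also infer something stronger: that effects are diluted by a known amount and the trial is underpowered. The documents do not support that. They do not say that benefit is confined to people with high PHS, they give no share of such people, and Section 7 itself separates OSA-related memory impairment from AD. Nothing makes loop gain, or the effect of oxygen on AHI, depend on PHS.

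**Conclusion.** The point holds as one of interpretation and generalisability. The people studied will be adults aged 65-85 with MoCA above 26, with or without OSA, of unspecified AD risk. *Unspecified* is the exact word: they are selected on age, cognition and, by aim, on OSA and predicted oxygen response, but not on AD risk. A conclusion about preclinical AD would have no support from such a sample, and at least two-thirds of Aim 4 would lack the imaging that Section 7 relies on. That share assumes the Section 11 numbers are met.

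The oxygen versus room air and oxygen versus PAP comparisons remain internally valid, as does the AHI result for the patients actually enrolled. The point rests on the readable text and would change if an unseen figure defined a selection step.

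**What to change.** Restate the population in the aims, hypotheses and conclusions as cognitively normal adults aged 65-85, with or without OSA, with PHS measured.

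In Section 10, turn the general intention about interactions into named terms: continuous PHS by OSA status for loop gain (Aim 1) and hippocampal volume (Aim 3), and continuous PHS by arm for the word pairs result (Aim 4). Report each as an estimate with a confidence interval and say that none is a powered test. Make PHS a fixed covariate in Aim 4, whether or not the arms are imbalanced.

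Two passages then need reconciling, because PHS would carry more weight: Section 9 describes saliva sent to a CLIA-certified laboratory, while Section 15 describes buccal swabs and testing outside a CLIA-approved laboratory. The Section 9 statement that PET covers people with memory impairment should also be squared with MoCA above 26.

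The cost is wording and a few prespecified model terms on data already collected. The downside is a more modest population claim. I would not add a PHS entry cut-off to save the label: Aim 4 already needs 60 oxygen-sensitive OSA patients, while Section 7 estimates about 30% responsive, or 0.30 × 65 = 19.5 of the 65 in Aim 2. A cut-off would shrink that pool further.
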